9.1.2. Prior and Concomitant Medications

Summaries of medications will be presented by WHO Drug Levels 1 and 2 and treatment group for participants in the safety population ([Table 69](#)). Individual participant listings will be presented for all concomitant medications ([Listing 32](#)).

9.2. Measurements of Treatment Compliance

The number of doses of study product administered to participants will be presented by treatment group as part of the participant disposition table ([Table 6](#)). [Table 9](#) presents the number of participants who received a first dose at each enrollment period by treatment group. A listing of treatment compliance data by participant will also be presented in [Listing 8](#).

9.3. Adverse Events

Unsolicited AEs and SAEs will be coded by MedDRA for preferred term (PT) and system organ class (SOC). AEs will also be graded for severity. For each AE experienced, the participant will be asked if he/she had received medical attention, defined as hospitalization, an ER visit, or an otherwise unscheduled visit to or from medical personnel for any reason. AEs characterized by such unscheduled medical care will be designated as MAAEs. Safety will be assessed by the frequency and severity of:

- Any AE related to 4CMenB immunization through the end of the study.
- Any AE related to rectal mucosal sampling procedures through the end of the study.
- Any SAEs through the end of the study

A summary of all adverse events is provided in **Table 51**. This information is also presented graphically in **Figure 88** with number and severity of AEs categorized by MedDRA System Organ Class and treatment group. A summary of those events that occurred in $\geq 5\%$ of participants in any treatment group is provided in **Table 54**.

9.3.1. **Solicited Events and Symptoms**

Systemic solicited adverse events were collected pre-vaccination, and systemic and local solicited adverse events were collected 30 minutes post-vaccination and then daily for 7 days after each vaccination and graded on a severity scale of 0 (absent), 1 (mild), 2 (moderate) and 3 (severe). Systemic events include fever, chills/shivering/sweating, fatigue, malaise, myalgia and arthralgia (exclusive of the injection site), headache, and nausea. Local events include pain at injection site, pruritus, erythema, ecchymosis, induration/swelling, pain, and tenderness. **Table 56** summarizes the solicited adverse event grading scale.

The proportion of participants reporting at least one solicited adverse event will be summarized for each solicited adverse event, any systemic symptom, any local symptom, and any symptoms. The 95% CI will be calculated using Clopper-Pearson methodology from a binomial distribution (**Table 55**).

For each systemic and local event, any systemic event, any local event, and any solicited event, the maximum severity over 7 days after each vaccination will be summarized for the safety population. The number and percentage of participants reporting each event will be summarized by the maximum severity and treatment group, separately for each vaccination and over all vaccinations. For each event the denominator is the number of participants with non-missing data for the specific event (**Table 55**).

The number of participants reporting a solicited adverse event will be summarized for each day post vaccination for each vaccination and for all vaccinations combined both in a summary table (**Table 56**, **Table 7**, **Table 58**, and **Table 59**) and graphically in a bar chart (**Figure 89** and **Figure 90**). A comparison of the event rate for each treatment group between dose 1 and dose 2 will be presented in **Table 60**.

Solicited adverse events by participant will be presented in **Listing 23** and **Listing 24**.

9.3.2. **Unsolicited Adverse Events**

When calculating the incidence of unsolicited AEs (i.e., on a per participant basis), each participant will only be counted once at the highest severity and/or relationship, and any repetitions of AEs within a participant will be ignored; the denominator will be the total number of participants in the safety population. All AEs reported will be included in the summaries and analyses.

The number and percentage of participants reporting at least one unsolicited AE will be summarized by MedDRA system organ class and preferred term. Denominators for percentages are the number of participants who received the study vaccination summarized. A 95% CI will be presented for the percentage of participants reporting any unsolicited AE (serious or non-serious) for each MedDRA system organ class and preferred term. A listing of all unsolicited AEs by participant will be presented in **Listing 25**, sorted by Treatment group, participant ID, and AE Number.

The following summaries for unsolicited adverse events will be presented by MedDRA system organ class, preferred term, and Treatment group:

- Participant incidence and total frequency of unsolicited adverse events with 95% CI (**Table 61**)
- Summary of severity and relationship to study product (**Table 62**)

- Participant incidence and total frequency of related unsolicited adverse events over time (Days 1-7) ([Table 63](#))
- Participant listing of death and serious adverse events ([Table 52](#))
- Participant listing of non-serious adverse events of moderate or greater severity ([Table 53](#))
- Bar charts of the frequency and incidence of non-serious adverse events by severity and MedDRA system organ class ([Figure 91](#) and [Figure 92](#))
- Bar charts of the frequency and incidence of non-serious adverse events by relationship and MedDRA system organ class ([Figure 93](#) and [Figure 94](#))

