6.3.3. Safety Population

The safety analysis population includes all participants who received at least one dose of study treatment. For analyses using the safety population, participants will be grouped by study treatment received.

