Notes: Denominators for percentages are the number of participants in the Safety Population who received both the first and second dose.

[x] participants did not get the second dose and are not included in this table.

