14.3.1.2 Unsolicited Adverse Events

Table 61: Summary of Unsolicited Adverse Events by MedDRA System Organ Class and Preferred Term, Dose Number, and Treatment Group

4CMenB													
MedDRA Preferred Term	MedDRA Preferred Term	Post Dose 1 (N=X)				Post Dose 2 (N=X)				Post Any Dose (N=X)			
		n	%	95% CI	Events	n	%	95% CI	Events	n	%	95% CI	Events
Any SOC	Any PT	x	xx	xx, xx	x	x	xx	xx, xx	x	x	xx	xx, xx	x
[SOC 1]	Any PT												
	[PT 1]												
	[PT 2]												
[SOC 2]	Any PT												
	[PT 1]												
	[PT 2]												
Placebo													
MedDRA System Organ Class	MedDRA Preferred Term	Post Dose 1 (N=X)				Post Dose 2 (N=X)				Post Any Dose (N=X)			
		n	%	95% CI	Events	n	%	95% CI	Events	n	%	95% CI	Events
Any SOC	Any PT	x	xx	xx, xx	x	x	xx	xx, xx	x	x	xx	xx, xx	x
[SOC 1]	Any PT												
	[PT 1]												
	[PT 2]												
[SOC 2]	Any PT												
	[PT 1]												
	[PT 2]												

Note: N = number of participants in the Safety Population who received the specified dose. This table presents number and percentage of participants. A participant is only counted once per PT/time point.

Table 62: Unsolicited Adverse Events by MedDRA System Organ Class and Preferred Term, Maximum Severity, Relationship, and Treatment Group

MedDRA System Organ Class	Preferred Term	Severity	4CMenB (N = X)						Placebo (N = X)						All Participants (N = X)					
			Related		Not Related		Total		Related		Not Related		Total		Related		Not Related		Total	
			n	%	n	%	n	%	n	%	n	%	n	%	n	%	n	%	n	%
Any SOC	Any PT	Any Severity	x	xx	x	xx	x	xx	x	xx	x	xx	x	xx	x	xx	x	xx	x	xx
		Mild	x	xx	x	xx	x	xx	x	xx	x	xx	x	xx	x	xx	x	xx	x	xx
		Moderate	x	xx	x	xx	x	xx	x	xx	x	xx	x	xx	x	xx	x	xx	x	xx
		Severe	x	xx	x	xx	x	xx	x	xx	x	xx	x	xx	x	xx	x	xx	x	xx
SOC 1	PT 1	Any Severity	x	xx	x	xx	x	xx	x	xx	x	xx	x	xx	x	xx	x	xx	x	xx
		Mild	x	xx	x	xx	x	xx	x	xx	x	xx	x	xx	x	xx	x	xx	x	xx
		Moderate	x	xx	x	xx	x	xx	x	xx	x	xx	x	xx	x	xx	x	xx	x	xx
		Severe	x	xx	x	xx	x	xx	x	xx	x	xx	x	xx	x	xx	x	xx	x	xx
	PT 2	Any Severity	x	xx	x	xx	x	xx	x	xx	x	xx	x	xx	x	xx	x	xx	x	xx
		Mild	x	xx	x	xx	x	xx	x	xx	x	xx	x	xx	x	xx	x	xx	x	xx
		Moderate	x	xx	x	xx	x	xx	x	xx	x	xx	x	xx	x	xx	x	xx	x	xx
		Severe	x	xx	x	xx	x	xx	x	xx	x	xx	x	xx	x	xx	x	xx	x	xx

Note: N = Number of participants in the Safety Population.

Table 63: Related Unsolicited Adverse Events Within 7 Days Post Dosing by MedDRA System Organ Class and Preferred Term, Dose, and Treatment Group

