[Implementation Note: Day x-y interval should correspond to period of collection for solicited symptoms, if applicable.]

Treatment Group	MedDRA System Organ Class	MedDRA Preferred Term	Day 1-7 Post Dose 1			Day 1-7 Post Dose 2			Within 7 Days Post Either Dose		
			n	%	Events	n	%	Events	n	%	Events
4CMenB (N = X)	Any SOC	Any PT	x	xx	x	x	xx	x	x	xx	x
	[SOC 1]	Any PT									
		[PT 1]									
		[PT 2]									
	[SOC 2]	Any PT									
		[PT 1]									
		[PT 2]									
Placebo (N=X)	Any SOC	Any PT	x	xx	x	x	xx	x	x	xx	x
	[SOC 1]	Any PT									
		[PT 1]									
		[PT 2]									

Note: N = Number of participants in the Safety Population. This table presents number and percentage of participants. For each time point, a participant is only counted once per PT.

Table 64: Laboratory Assessment --RPR Results - Safety Population

Time Point	Treatment Group	N	Positive		Negative		Missing	
			n	%	n	%	n	%
Baseline	4CMenB	X	X	XX	X	XX	X	XX
	Placebo							
Day 29	4CMenB							
	Placebo							
Day 181	4CMenB							
	Placebo							
Max Severity Post Baseline	4CMenB							
	Placebo							

Note: N = Number of available participants in the Safety Population at certain time

Table of Figures (continued)

Table 65: Laboratory Assessment --HIV Antibody Testing Results - Safety Population

Time Point	Treatment Group	N	Positive		Negative		Missing	
			n	%	n	%	n	%
Baseline	4CMenB	x	x	xx	x	xx	x	xx
	Placebo							
Day 181	4CMenB							
	Placebo							
Max Severity Post Baseline	4CMenB							
	Placebo							

Note: N = Number of available participants in the Safety Population at certain time

Table of Figures (continued)

Table 66: Laboratory Assessment – Chlamydia NAAT Testing Results - Safety Population

Test	Time Point	Treatment Group	N	Positive		Negative		Missing	
				n	%	n	%	n	%
Chlamydia NAAT Genitourinary	Baseline	4CMenB	x	x	xx	x	xx	x	xx
		Placebo							
	Day 29	4CMenB							
		Placebo							
	Day 181	4CMenB							
		Placebo							
Chlamydia NAAT Rectal	Baseline	4CMenB							
		Placebo							
	Day 29	4CMenB							
		Placebo							
	Day 181	4CMenB							
		Placebo							
Chlamydia NAAT Pharyngeal	Baseline	4CMenB							
		Placebo							
	Day 29	4CMenB							
		Placebo							
	Day 181	4CMenB							
		Placebo							

Note: N = Number of available participants in the Safety Population at certain time

Table of Figures (continued)

Table 67: Laboratory Assessment – Gonorrhea NAAT Testing Results - Safety Population

Test	Time Point	Treatment Group	N	Positive		Negative		Missing	

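### SAP 9.3.2 sets two denominators for unsolicited adverse events, and the Table 63 shell would divide its post-dose-2 counts by everyone given at least one dose

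*SAP*

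**What the plan says.** SAP 9.3.2 (Unsolicited Adverse Events) opens with incidence per participant, each person counted once at the worst severity or relationship, and says that "the denominator will be the total number of participants in the safety population". The next paragraph, on the number and percentage of participants with at least one unsolicited event by MedDRA class and term, says: "Denominators for percentages are the number of participants who received the study vaccination summarized". Neither sentence is tied to particular tables.

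SAP 6.3.3 defines the population: "The safety analysis population includes all participants who received at least one dose of study treatment". It therefore includes people who never receive dose 2.

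The shells in SAP Appendix 1 differ in the same way:

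- Table 61 (all unsolicited events, by dose) has a separate N above each dose column, with the note "N = number of participants in the Safety Population who received the specified dose".
- Table 63 (related unsolicited events within 7 days, by dose) has a column headed "Day 1-7 Post Dose 2" but only one N per treatment group, with the note "N = Number of participants in the Safety Population. This table presents number and percentage of participants".
- Tables 55 and 56 (solicited events) define N as those given the dose concerned. Table 60 is limited to people who had both doses, and its footnote leaves a count to fill in: "participants did not get the second dose and are not included in this table".

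**The concern.** Someone who never received dose 2 cannot have an event in the week after it. If that person stays in the denominator of a post-dose-2 percentage, they are scored as event-free and the percentage falls. The error can only go downward, and it affects the post-dose-2 column but not the post-dose-1 column, so it also disturbs the dose-1 versus dose-2 comparison that the table sets up. With arms of 40 and 10, one missed dose has a different effect in each arm, so the between-arm comparison in that column is disturbed too.

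The programmer also has a practical problem. Section 9.3.2 supplies two written rules, and the two by-dose tables of unsolicited events each follow a different one.

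**Working it through.** **Inputs.** Planned arm sizes are 40 and 10 (SAP section 5); 50 subjects at 4:1 gives 50 × 4/5 = 40 and 50 × 1/5 = 10. I take these as the safety population sizes, assuming that every randomised person gets dose 1. The documents give no expected number of missed second doses. They do foresee some: protocol 8.6.2 lists grounds for withholding the second vaccination, and the Table 60 footnote has a place to count them. I use 0, 1 and 2 missed per arm, plus 4 of 40 in the 4CMenB arm, as assumptions. The participant counts with an event (10 on 4CMenB, 2 on placebo) are hypothetical. The plan attaches no figure of its own to this point, so there is none to reproduce.

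**Formula.** Let x be the number of participants with a post-dose-2 event, N the safety population in the arm, and n2 the number given dose 2.

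- Percentage under the Table 63 note: x / N
- Percentage among those given dose 2: x / n2
- Relative understatement: 1 − (x/N) / (x/n2) = 1 − n2/N, the share of the arm missing dose 2, whatever x is.

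**Results.**

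| Arm | n2 | Relative understatement | Table 63 as written | Dose-2 recipients | Difference (points) |
|---|---|---|---|---|---|
| 4CMenB, N = 40, x = 10 | 40 | 0% | 25.0% | 25.0% | 0.0 |
| | 39 | 1 − 39/40 = 2.5% | 25.0% | 25.6% | 0.6 |
| | 38 | 1 − 38/40 = 5% | 25.0% | 26.3% | 1.3 |
| | 36 | 1 − 36/40 = 10% | 25.0% | 27.8% | 2.8 |
| Placebo, N = 10, x = 2 | 10 | 0% | 20.0% | 20.0% | 0.0 |
| | 9 | 1 − 9/10 = 10% | 20.0% | 22.2% | 2.2 |
| | 8 | 1 − 8/10 = 20% | 20.0% | 25.0% | 5.0 |

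**Effect on comparisons.** One missed dose moves the placebo figure four times as much in relative terms as the 4CMenB figure (10% against 2.5%). With one missed in each arm, the post-dose-2 gap between arms is 25.0 − 20.0 = 5.0 points as written, and 25.6 − 22.2 = 3.4 points among those dosed. Within the 4CMenB arm, if 10 people have an event after each dose and two miss dose 2, the table shows 25.0% and 25.0% where dose-specific denominators give 25.0% and 26.3%.

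**What is not touched.** For post-dose-1 and either-dose columns, the people given the relevant vaccination are the whole safety population, so the two rules coincide. Tables 51 and 62 are not split by dose and use the safety population, which is right for them.

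**The case against.** The two rules can be read together. The first describes counting people once at their worst severity or relationship, which matches Table 62. The second refers to the vaccination summarised, which matches by-dose tables such as Table 61. On that reading the SAP body already prescribes the right denominator and one table note is out of step. This is a fair account of what was probably meant, but the SAP does not say it. Its list of outputs describes both Table 61 and Table 63 as participant incidence, the term used in the first rule. Even on the charitable reading, Table 63 departs from the second rule.

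The Table 63 note defines N but, unlike the Table 60 note, does not state outright what percentages are divided by. That is so. With one N per group and no other count shown, division by it is the natural reading, though still an inference.

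The effect may be nil or very small. That stands. If everyone receives dose 2 the figures are identical, and SAP 6.5 expects little missing data. Table 63 has no confidence intervals and the study tests no formal hypothesis. A reader could also recompute the percentage from n in Table 63 and the dose-2 N printed in Tables 55 and 61.

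Three stronger readings are tempting and do not hold:

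- *That Tables 61 and 63 would report contradictory rates for the same thing.* Table 61 covers all unsolicited events with no 7-day limit, while Table 63 covers related events in Days 1-7. Their percentages would differ even with a common denominator. What conflicts is the choice of denominator.
- *That the secondary safety endpoint is biased.* That endpoint is related events through the end of the study, and Tables 51 and 62 carry it with a suitable denominator.
- *That the understatement could be 25% and 40%, from the 30/6 row of protocol Table 2.* That row explores participants without usable immunogenicity data for the primary analysis. It says nothing about missed vaccinations.

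**Conclusion.** Wrong as written, and minor. The two denominator rules in SAP 9.3.2 are unreconciled, and the Table 63 shell applies the at-least-one-dose population to a post-dose-2 percentage, against the convention of Tables 55, 56, 60 and 61.

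Followed as written, the post-dose-2 percentage is understated by exactly the proportion of the arm that misses dose 2. Under the assumed one or two missed doses and the hypothetical counts above, that is about 0.6 to 1.3 percentage points for 4CMenB and 2.2 to 5.0 points for placebo. The conclusion about direction needs no assumption about event rates. The size depends wholly on how many miss dose 2, which the documents do not give. The damage is confined to one column of one descriptive table and the comparisons made from it. No test, sample size, primary result or overall related-event summary changes.

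**What to change.** In SAP 9.3.2, limit the safety population denominator to any-dose and overall summaries. State that post-dose-1 and post-dose-2 percentages, and any confidence intervals given with them, are based on the safety population participants who received that dose.

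In the Table 63 shell, replace the single N per group with a separate N for each of the post-dose-1, post-dose-2 and either-dose columns. Use the Table 61 note wording for the two dose columns and keep the safety population for the either-dose column. The percentages apply to participants; the Events column needs no denominator.

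The cost is a sentence or two in the SAP text, one table header and one note. No new data are needed, since the dose-2 count is already required for Tables 55 and 61.

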9.4. Pregnancies

For any participants in the safety population who become pregnant during the study, every attempt will be made to follow these participants to completion of pregnancy to document the outcome, including information regarding any complications with pregnancy and/or delivery. A listing of pregnancies and outcomes will be presented in [Listing 33](#), [Listing 34](#), [Listing 35](#), [Listing 36](#), and [Listing 37](#).

9.5. Clinical Laboratory Evaluations

Clinical laboratory evaluations assessed at the screening visit will be considered as baseline. At the screening visit (visit 00A), the following clinical laboratory parameters will be evaluated: a serology screening (HIV-1/2 and RPR), GC/CT NAAT at mucosal sites (rectum, vagina and oropharyngeal), and Trichomonas NAAT for female participants. For the rectal mucosal biopsy cohort, hematology (CBC) and coagulation testing (PT/aPTT) will be measured at visit 00A and may be repeated at visit 00B. At day 29, before the second vaccination and final visit at day 181 or early termination visit, serology screening (HIV-1/2 and RPR) and GC/CT NAAT at mucosal sites will be evaluated again. The laboratory adverse event grading scale will be presented in [Table 5](#).

RPR, HIV antibody and STI testing will be presented in [Table 64](#), [Table 65](#), [Table 66](#), [Table 67](#), and [Table 69](#). A complete listing of individual laboratory results will be presented in [Listing 26](#) and [Listing 27](#). Participants with abnormal laboratory results, grade 1 severity or higher, will be presented in [Listing 28](#) and [Listing 29](#), for hematology and coagulation, respectively, sorted by participant ID, parameter, and study day.

9.6. Vital Signs

Vital signs will be assessed at screening visits (Visit 00A or, if performed, Visits 00B and/or 00C), baseline visit (Visit 1, day 1), day 29 and 43, and possibly at other visit determined by study staff. Enrolled participants with abnormal vital signs will be listed ([Listing 30](#)).

9.7. Physical Examinations

Physical examinations will be performed at screening visit 00A, and possibly at every visit as determined by study staff. Physical examination will include the following organs and organ systems: general appearance, head /eyes /ears /nose /throat (HEENT), neck, lungs, heart, abdomen, extremities, musculoskeletal, lymph nodes, skin, and nervous system. Genital and rectal exams will be performed at the investigator's discretion ([Listing 31](#)).

9.8. Concomitant Medications

Concomitant medications will be coded to the Anatomical Therapeutic Classification (ATC) using the WHO Drug Dictionary. The use of prior and concomitant medications taken during the study will be recorded on the CRFs. A by-participant listing of concomitant medication use will be presented in [Listing 32](#). The use of concomitant medications during the study will be summarized by ATC1, ATC2 code and treatment group for the Safety population ([Table 69](#)).

9.9. Other Safety Measures

There are no other safety measures performed.

10. OTHER ANALYSES

Not applicable

11. REPORTING CONVENTIONS

The mean, geometric mean, standard deviation, and other statistics will be reported to one decimal place greater than the original data. The minimum and maximum will use the same number of decimal places as the original data. Proportions will be presented as two decimal places; values greater than zero but <0.01 will be presented as “<0.01”. Percentages will be reported to the nearest whole number; values greater than zero but <1% will be presented as “<1”; values greater than 99% but less than 100% will be reported as >99%. Estimated parameters, not on the same scale as raw observations (e.g. regression coefficients) will be reported to three significant figures.

12. TECHNICAL DETAILS

SAS version 9.4 or above will be used to generate all tables, figures and listings. R studio may also be used to generate figures.

**13. SUMMARY OF CHANGES IN THE CONDUCT OF THE STUDY OR
PLANNED ANALYSES**

There are no changes in the conduct of the study. With the protocol amendment from v6.0 to v7.0, an interim immunogenicity analysis was added. A separate interim immunogenicity report will be developed for this analysis.

15. LISTING OF TABLES, FIGURES, AND LISTINGS

Table, figure, and listing shells are presented in Appendices 1, 2, and 3.

APPENDICES

9.1 Overall Study Design and Plan Description

Table 1: Study Design

	Rectal Mucosal Biopsy Cohort (N=20)*		No Rectal Mucosal Biopsy Cohort (N=30) *		Total
Vaccine	Male	Non-pregnant Female	Male	Non-pregnant Female	
4CMenB	8	8	12	12	40
Placebo	2	2	3	3	10

*As noted in the study design, this trial will enroll approximately 50 (maximum of 60 participants) - approximately 20 in Rectal Mucosal Biopsy Cohort and approximately 30 in No Rectal Mucosal Biopsy Cohort

